**Week 26 (Visit 3)**

- Record medical history (exacerbation, antibiotics?)
- Assessment of LRTI-VAS
- Quality of Life-Bronchiectasis (QOL-B) questionnaire
- Leicester cough score
- Physical examination (including sputum characteristics, cough, dyspnoea, pleuritic chest pain, chills or rigors, and lung sounds) and vital signs (respiratory rate, heart rate, blood pressure, body temperature and oxygen saturation)
- Diary card check
- Repeat laboratory examination (CRP, Hb, WBC, Sodium, Potassium, Creatinin, eGFR, Liver Function)
- Sputum examination for microbiologic assessment
- Spirometry according to the standard criteria of the European Respiratory Society
- Potential side effects will be recorded
- Dispense study medication
- Remaining study drug is collected and/or is sent to Noordwest Ziekenhuisgroep location Alkmaar

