Efficacy parameters will include assessment of pulmonary exacerbations, spirometry, LTRI-VAS, QOL-B and Leicester cough questionnaires. Microbiological response measurements will include semi-quantitative density of pathogens in sputum, including the tobramycin minimum inhibitory concentration (MIC) for isolated pathogens. Safety parameters will include assessment of AEs, serial spirometry findings, clinical laboratory test results, vital signs measurements, physical examination. Study drug is dispensed on the regular visits. The first patients will be enrolled in the summer of 2016, with a treatment period of 12 months, we expect to terminate the study 31-01-2020.

In subjects who experience a pulmonary exacerbation, every effort should be made to continue their allocated inhaled study drug, unless the study drug is not tolerated, or the pulmonary exacerbation is believed to be related to study drug. All subjects who receive any study drug need to complete the visit 7 assessments. Subjects who are prematurely withdrawn from study drug will be encouraged to

remain in the study and attend subsequent study visits; at a minimum, they should complete the visit 7 assessments as an early termination visit.

An independent expert will be established to conduct periodic reviews of subject safety for this protocol. The independent expert will also perform a blinded analysis of the pulmonary exacerbation data to check whether the assumptions for sample size estimation are valid, and if they are not, the sample size may be increased.

This study will be conducted in the Noordwest Ziekenhuisgroep, Canisius ZH Nijmegen, Spaarne Gasthuis Hoofddorp, Zuyderland MC Heerlen, VU Medical Center Amsterdam and UMC Utrecht.

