#### 6.2.2 Sputum Concentrations

Ten minutes after inhalation of the first 300 mg dose of tobramycin inhalation solution, the average concentration of tobramycin was 1237 mcg/g (ranging from 35 to 7417 mcg/g) in sputum^37.

Tobramycin does not accumulate in sputum; after 20 weeks of therapy with the tobramycin inhalation solution regimen, the average concentration of tobramycin at ten minutes after inhalation was 1154 mcg/g (ranging from 39 to 8085 mcg/g) in sputum. High variability of tobramycin concentration in sputum was observed. Two hours after inhalation, sputum concentrations declined to approximately 14% of tobramycin levels at ten minutes after inhalation.

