#### **6.5 Description and justification of route of administration and dosage**

TIS UPS is produced and packed by TEVA Pharmaceuticals in accordance to the principles and the detailed guidelines of Good Manufacturing Practice for Medicinal Products and will be delivered at the pharmacy of Stichting Haarlemse Ziekenhuizen. All the public information about the investigational product is written in the SPC-document. TIS is packaged in small plastic ampules (miniplasco's) of 5 ml; each ampule contains one full dose of tobramycin (300mg). These ampules are packed in identical sealed boxes. The investigators will be blinded for the content of the boxes. The placebo is a plastic ampule of NaCl 0.9% 5ml. These ampules are also called miniplasco's. The placebo is produced by Centrafarm B.V in accordance to the principles and detailed guidelines of Good Manufacturing

Practice for Medical Products. Also, these ampules will be delivered at the pharmacy of Haarlemse Ziekenhuizen. The shape of the ampules of the placebo (NaCl 0.9%) is different from the ampules of TIS, therefore the ampules will be packed in identical sealed boxes. The investigators will be blinded for the content of the boxes, in this way the blind will remain existent.

Labelling will be done at the pharmacy of Haarlemse Ziekenhuizen. The ampules remain intact, and a new label is printed on the package in accordance with the guidelines Good Manufacturing Practice. The expiration date, reference code and batch code are printed on the ampules and sealed boxes. The 300mg dose of tobramycin inhalation solution (or placebo) is the same for patients regardless of age or weight. Doses should be inhaled as close to 12 hours apart as possible and not less than 6 hours apart. In this study TIS is used once daily in the morning. The pharmacy of Haarlemse Ziekenhuizen is responsible for the labelling and packaging of the sealed boxes for both TIS and placebo. These labelled and sealed boxes are sent to the pharmacy of the Noordwest Ziekenhuisgroep, location Alkmaar. The transportation is under refrigeration at 2-8°C/36-46°F. The storage of the investigational product (TIS or placebo) is under refrigeration at 2-8°C/36-46°F with 2-year shelf life at these circumstances. Temperature will be monitored continuously.

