#### **7.1.2 Secondary study parameters/endpoints (if applicable)**

The secondary objective of this study is to evaluate the effect of TIS treatment on time to next exacerbation, airflow limitation (FVC% predicted, FEV1% predicted), LRTI-VAS, Quality of Life-Bronchiectasis (QOL-B), Leicester cough score, bacterial load in sputum and tobramycin resistance, including MIC values, depending on the capabilities of the microbiological laboratory.

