## **7.3 Study procedures**

Patients with bronchiectasis and who fulfil the inclusion and exclusion criteria will be asked to participate in the study. After a run-in period of 4 weeks' patients will be randomized to receive one of the two possible treatment regimens: TIS OD 300 mg daily or placebo. Administration will be continuous for the full 12 months. According to the parallel group design patients will be treated for 52 weeks. After completing the intervention period patients will have a follow-up (wash out period) of 4 weeks. This wash-out period was considered to be one month, in which time the antimicrobial effect of the antibiotic supposedly disappears, as suggested in earlier studies.

Subjects will be evaluated at run-in = visit 0 (week -4), visit 1 (day 1- start of the study), visit 2 (week 13), visit 3 (week 26), visit 4 (week 39), visit 5 (week 52: end of treatment) and visit 6 (run-out; week 56: end of the study). One week after start of treatment a phone call will be scheduled. Clinical, laboratory, and bacteriology evaluations will be determined according to the schedule (Figure 1: study schedule). Subjects who terminate treatment should be followed for the same period as those who complete the study, according to the study schedule.

During the study any changes in medical condition and compliance with medication will be filed in the diary card.

At visit 1, after randomisation, a tolerance test with either TIS or placebo (blinded according to randomisation) will be performed. Before nebulizing TIS patients are treated with salbutamol 200mcg using an AeroChamber. During tidal breathing patients inhale 300mg TIS or placebo (at room temperature) by using the Innospire Deluxe nebulizer with mouthpiece during approximately 5 minutes. If patients develop a moderate-severe bronchial obstruction, patients are excluded from the study. The severity of bronchial obstruction and coughing is assessed by a specialized nurse, the respiratory physician or the own GP. An exacerbation is defined as the presence of three or more of the following symptoms or signs for at least 24 hours: increased cough, increased sputum volume, increased sputum purulence, haemoptysis, increased dyspnoea, increased wheezing, fever (>38.5°C)

or malaise, and the treating physician agreed that antibiotic and/or prednisolone therapy was required.

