#### **Run-in (Visit 0, week -4)**

At the baseline visit (- 4 weeks), subjects will be deemed eligible for the study after the clinical diagnosis bronchiectasis has been made, and the study has been explained to them. The following procedures will be completed:

- Verify inclusion/exclusion criteria
- Obtain written informed consent (alternatively at visit 1)
- Record medical history
- Collection of demographic information, concurrent disease, concomitant medication use, and previous course(s) of antibiotic therapy in the preceding year
- Physical examination (including sputum characteristics, cough, dyspnoea, pleuritic chest pain, chills or rigors, and lung sounds) and vital signs (respiratory rate, heart rate, blood pressure, body temperature and oxygen saturation)
- Laboratory examination (CRP, Hb, WBC, Sodium, Potassium, Creatinin, eGFR, Liver Function Tests, extra blood sample(s) will be taken and frozen for future research)
- Sputum culture (semi-quantitative)
- Randomisation (or at visit 1)

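### Sputum for bacterial load and tobramycin resistance at weeks 26 and 52 has no stated timing relative to the morning inhalation, so samples in the TIS arm can carry drug into the culture

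*Combined protocol and SAP*

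**What the plan says.** Section 7.1.2 lists among the secondary endpoints "bacterial load in sputum and tobramycin resistance, including MIC values, depending on the capabilities of the microbiological laboratory". Section 3 describes the measurement: "Microbiological response measurements will include semi-quantitative density of pathogens in sputum", together with the tobramycin MIC of the isolated pathogens.

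Section 7.3 schedules sputum four times: at visit 0 before any study drug, at weeks 26 and 52 on treatment, and at week 56 after the wash-out. For weeks 26 and 52 the full instruction is "Sputum examination for microbiologic assessment". On dosing, section 6.5 states: "In this study TIS is used once daily in the morning". Patients take the drug themselves, and the only dose that must be supervised is the one on day 1.

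The visible text does not set a sampling time relative to the dose, and it does not ask for the time of the last inhalation. Nor does it describe how the laboratory deals with tobramycin present in a specimen. The diary card and the ampule count in section 6.8 track compliance, but neither is said to capture the hour of a dose. Section 9.4 names no specific analysis for load or resistance.

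**The concern.** Semi-quantitative culture measures what grows from the specimen. If the specimen contains tobramycin, susceptible organisms may fail to grow even though they are alive in the airway, while resistant ones still grow. Placebo sputum contains no study tobramycin, so randomisation and blinding do not balance the effect between arms.

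Two distortions are possible, both confined to the TIS arm. Load may look lower than it is, which favours TIS. The tobramycin-resistant share of what grows may look higher, because the susceptible isolates that would have received an MIC are missing.

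The visit 0 and week 56 samples are free of carry-over. Section 7.3 describes the wash-out as a period "in which time the antimicrobial effect of the antibiotic supposedly disappears". A change from baseline to week 26 or 52, or a rebound from week 52 to week 56, could thus mix a real airway effect with a laboratory artefact. Without recorded times the two cannot be separated afterwards.

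**Working it through.** The plan gives no figure of its own for residual drug at sampling, so there is none to reproduce. The check uses the protocol's background data.

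**Inputs**
- Section 6.2.2, ten minutes after the first 300 mg dose: "the average concentration of tobramycin was 1237 mcg/g (ranging from 35 to 7417 mcg/g) in sputum". After 20 weeks the mean at the same time point is 1154 mcg/g (39 to 8085). The 20-week value is the closer match for weeks 26 and 52.
- Section 6.2.2, decline: "Two hours after inhalation, sputum concentrations declined to approximately 14% of tobramycin levels at ten minutes after inhalation".
- Section 6.3: 16 mcg/mL is the MIC level used to describe raised MICs in *P. aeruginosa*.
- Section 1: the sputum half-life of TIS in non-CF bronchiectasis is unknown.
- Assumption: 1 mcg/g of sputum is roughly 1 mcg/mL.

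**Step 1. Residual drug at two hours (no decay model needed)**
- After 20 weeks: 0.14 x 1154 = 162 mcg/g, and 162 / 16 = 10.1.
- After the first dose: 0.14 x 1237 = 173 mcg/g, and 173 / 16 = 10.8.
- Across the 20-week range: 0.14 x 39 = 5.5 mcg/g to 0.14 x 8085 = 1132 mcg/g.

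The mean is about ten times the 16 mcg/mL level. The lower end of the range is already below it.

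**Step 2. How long the mean stays above 16 mcg/g (model-dependent)**

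*One-phase decay.* k = -ln(0.14) / 110 min = 0.0179 per min, a half-life of ln(2) / k = 38.8 min. Time to 16 mcg/g = 10 min + ln(C / 16) / k:
- C = 1154: 249 min, about 4.2 h
- C = 39: about 1.0 h
- C = 8085: about 6.0 h

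*Slower late phase.* Assume a half-life of 2 h or 4 h from the two-hour point onwards. Since log2(162 / 16) = 3.34:
- 2 h half-life: 2 + 2 x 3.34 = 8.7 h
- 4 h half-life: 2 + 4 x 3.34 = 15.3 h

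**Step 3. Residual at 24 h, as for a sample taken before that day's dose**

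| Assumed decay | Mean (from 1154 mcg/g) | Top of range (from 8085 mcg/g) |
|---|---|---|
| One phase, 38.8 min | practically zero | practically zero |
| Late half-life 2 h | 162 x 0.5^11 = 0.08 mcg/g | 1132 x 0.5^11 = 0.55 mcg/g |
| Late half-life 4 h | 162 x 0.5^5.5 = 3.6 mcg/g | 1132 x 0.5^5.5 = 25 mcg/g |

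Under every assumption a pre-inhalation sample carries far less drug than one taken two hours after a dose. Whether it carries none depends on the late phase, which the documents do not give.

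**The case against.** Several points on the other side stand.

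- **Timing in practice.** The documents give neither clinic hours nor the hour of home dosing. A reader might infer that most samples will be taken a few hours after inhalation, so that a typical TIS sample is contaminated. That is not stated anywhere, and a mean with so wide a range around it does not describe a typical patient.
- **Kinetics.** Section 6.2.2 does not name its population, and section 1 says that antibiotic pharmacokinetics differ between CF and non-CF bronchiectasis. A curve through two points, one of them approximate, cannot settle the 24 h value.
- **Culture method.** Plating and dilution are not described. A concentration in raw sputum above an MIC does not prove inhibition on the plate.
- **True effect.** Section 6.3 reports that density fell on drug and returned to baseline off drug. A real fall and a real rebound are therefore to be expected, and carry-over would only add to them.
- **Week 52.** Section 7.3 calls this visit the end of treatment and has the drug, nebulizer and compressor collected. Whether a dose is due that morning is not stated.
- **Study schedule.** Section 7.3 refers to Figure 1 for bacteriology. The figure is not visible here and may hold a timing note.

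These points limit how likely and how large the distortion is. They do not close the gap: the visible text permits a sample soon after inhalation, and nothing recorded would reveal it.

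A reader might also extend the point to FEV1 and FVC. The documents do not support that. It would require reading the order of the visit 1 list as a sequence in time, yet the visit 0 list puts the eligibility check before consent. Spirometry also follows external European Respiratory Society criteria that are not reproduced in the protocol.

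**Conclusion.** The point holds as a possible bias in two secondary microbiological endpoints, in the TIS arm only. Bacterial load may read too low and the resistant share too high. The firm figure is a mean of about 162 mcg/g at two hours, about ten times 16 mcg/mL. It rests on section 6.2.2 applying to this population and on mcg/g being close to mcg/mL.

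The size of any false drop cannot be computed. Clinic times, culture method and non-CF sputum half-life are all missing, and part of any fall will be true drug effect. The documents do not support saying that the endpoints are biased, or that an observed drop at weeks 26 and 52 is an artefact. The primary exacerbation endpoint is untouched. The change is worth making because it costs little and the problem cannot be repaired later without recorded times.

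**What to change.** - In section 7.3, for weeks 26 and 52 and identically in both arms, state that sputum is collected before any inhalation taken that day. This fixes the order of sampling and leaves the dosing rule unchanged.
- State whether a dose is due on the day of the week 52 visit, so that the end-of-treatment label, the collection of drug and equipment, and the sampling instruction agree.
- Record in the e-CRF the time of the last inhalation and the time of the sputum sample.
- Flag samples taken after a same-day inhalation, and pre-specify a sensitivity analysis of load and resistance without them.
- If Figure 1 already gives a sampling time, repeat it in section 7.3.

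The cost is two data fields and a fixed order of procedures at two visits, with no extra visit or test. Sections 4.4 and 9.1 suggest that the trial may already be under way. If so, samples taken before the change will have no recorded timing and should be reported as such.

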**Week 39 (Visit 4)**

- Record medical history (exacerbation, antibiotics?)
- Diary card check
- Repeat laboratory examination (CRP, Hb, WBC, Sodium, Potassium, Creatinin, eGFR, Liver Function)
- Potential side effects will be recorded
- Dispense study medication
- Remaining study drug is collected and/or is sent to Noordwest Ziekenhuisgroep location Alkmaar

**Week 52 (Visit 5)**

- Record medical history (exacerbation, antibiotics?)
- Assessment of LRTI-VAS
- Quality of Life-Bronchiectasis (QOL-B) questionnaire
- Leicester cough score
- Physical examination (including sputum characteristics, cough, dyspnoea, pleuritic chest pain, chills or rigors, and lung sounds) and vital signs (respiratory rate, heart rate, blood pressure, body temperature and oxygen saturation)
- Diary card check
- Repeat laboratory examination (CRP, Hb, WBC, Sodium, Potassium, Creatinin, eGFR, Liver Function Tests, extra blood sample(s) will be taken and frozen for future research)
- Sputum examination for microbiologic assessment
- Spirometry according to the standard criteria of the European Respiratory Society
- Potential side effects will be recorded
- Remaining study drug, nebulizer, and compressor are collected

**Week 56 (run out, Visit 6)**

- Record medical history (exacerbation, antibiotics?)
- Assessment of LRTI-VAS
- Quality of Life-Bronchiectasis (QOL-B) questionnaire
- Leicester cough score
- Diary card check
- Repeat laboratory examination (CRP, Hb, WBC, Sodium, Potassium, Creatinin, eGFR, Liver Function)
- Sputum examination for microbiologic assessment
- Spirometry according to the standard criteria of the European Respiratory Society

**7.4 Withdrawal of the individual subjects**

Subjects can quit the study at any time for any reason if they wish to do so without any consequences. The investigator/treating physician can decide to withdraw a subject from the study for urgent medical reasons.

### **7.5 Replacement of individual subjects after withdrawal**

We estimate a drop-out of 30% patients. The number of potentially lost patients has been added to the number patients required by sample size calculation.

### **7.6 Follow-up of subjects withdrawn from treatment**

Follow-up of patients withdrawn from treatment have an out-patient visit following the study schedule. These patients will be evaluated the same as the patients who complete the study. Subjects will be evaluated at run-in = visit 0 (week -4), visit 1 (day 1- start of the study), visit 2 (week 13), visit 3 (week 26), visit 4 (week 39), visit 5 (week 52: end of treatment) and visit 6 (run-out; week 56: end of the study). One week after start of treatment a phone call will be scheduled. During an exacerbation the patient will contact his/her own GP or specialist.

### **7.7 Premature termination of the study**

With the expertise of maintenance treatment in CF patients and non-CF patients it is not likely that side effects may be a reason for termination of the study. If the independent expert sees any issues with safety regarding this clinical trial the study may be suspended or terminated for further/interim analysis by an independent statician. If he has serious concerns about safety of study subjects he will report these to the METC.

## **8. SAFETY REPORTING**

### **8.1 Section 10 WMO event**

In accordance to section 10, subsection 1, of the WMO, the investigator will inform the subjects and the reviewing accredited METC if anything occurs, on the basis of which it appears that the disadvantages of participation may be significantly greater than was foreseen in the research proposal. The study will be suspended pending further review by the accredited METC, except in so far as suspension would jeopardise the subjects' health. The investigator will take care that all subjects are kept informed.

### **8.2 AEs, SAEs and SUSARs**

#### **8.2.1 Adverse events (AEs)**

Adverse events are defined as any undesirable experience occurring to a subject during the study, whether or not considered related to the investigational product / the experimental intervention. All adverse events reported spontaneously by the subject or observed by the investigator or his staff will be recorded. Only AE's related to study procedures or medication will be recorded and reported once a year.

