### **8.4 Follow-up of adverse events**

All AEs will be followed until they have abated, or until a stable situation has been reached. Depending on the event, follow up may require additional tests or medical procedures as indicated, and/or referral to the general physician or a medical specialist.

SAEs need to be reported till end of study within the Netherlands, as defined in the protocol.

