### **8.5 Safety Committee/ Independent expert**

The safety committee consist of one member, called the independent expert who is independent of the set-up and execution of the trial. This independent expert will receive the definite protocol and all revisions. The independent expert will convene every three to six months and review the results, i.e. results split by experimental and control arms. The independent expert has the power to recommend termination of the study based on the evaluation of these results. There are typically three reasons an independent expert might recommend termination of the study: safety concerns, outstanding benefit, and futility. The primary mandate of this independent expert is to protect patient safety. If adverse events of a particularly serious type are more common in the experimental arm compared to the control arm, then the independent expert would have to strongly consider termination of the study. This evaluation has to be made in consideration of risk/benefit. In many cases, the experimental arm could cause serious adverse events, but the resulting improvement in survival could outweigh these adverse events.

The independent expert should inform the findings or conclusions to the study investigators by mail or e-mail. If there is any dispute between the independent expert and study investigators, the independent expert should notify the METC Noord-Holland.

The independent expert is:

[name] longarts, Heiloo

Email: [contact]

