### **11.2 Monitoring and Quality Assurance**

The conduct of the study and data entries will be monitored by an external monitor, [name]. He will select a sample of cases and check them for irregularities. If any are found, the monitor may choose to select a larger sample or review all available data. He will report the irregularities to the sponsor who is responsible for correcting any mistakes.

All adverse events will be analysed periodically by the statistician of the DSMB. If SAE's or SUSARs are more common in the experimental arm compared to the control arm he will inform the sponsor and other members of the DSMB which may then take actions as described in chapter 8.5. All serious adverse events will be reported to the accredited METC.

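### Section 8.2.1 gives two conflicting rules for recording adverse events, so a site could leave non-serious events judged unrelated out of the AE record

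*Combined protocol and SAP*

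**What the plan says.** Section 8.2.1 defines an adverse event as any undesirable experience during the study, "whether or not considered related to the investigational product / the experimental intervention". It then gives a recording rule: "All adverse events reported spontaneously by the subject or observed by the investigator or his staff will be recorded". The sentence directly after it gives another: "Only AE's related to study procedures or medication will be recorded and reported once a year".

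Other sections bear on which rule is meant:

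- Section 3 lists AEs as a safety parameter with no limit to related events: "Safety parameters will include assessment of AEs, serial spirometry findings, clinical laboratory test results".
- Section 8.4: "All AEs will be followed until they have abated, or until a stable situation has been reached".
- Section 11.2: "All adverse events will be analysed periodically by the statistician of the DSMB".
- Section 8.5 has the independent expert "review the results, i.e. results split by experimental and control arms".
- In section 7.3, the lists for visits 2 to 5 ask only for potential side effects. The week-1 phone call is likewise worded around effects of the study medication. The week-56 list has no adverse-event line.
- The closing summary of section 8.2.3 describes patients reporting adverse effects or events of the study drug.
- Sections 8.2.2 and 11.2 require reporting of serious adverse events with no relatedness condition.

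**The concern.** The definition and the first rule do not depend on causality; the second rule does. If recording depends on a causality opinion, an event judged unrelated is missing from the AE record, and a later comparison of arms cannot show whether such events were more frequent on tobramycin.

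That judgement is hard to make in this trial. The Summary names cough, wheezing and dyspnoea as adverse effects of the treatment, and section 7.3 uses increases in the same symptoms as exacerbation criteria. One clinician may attribute a symptom to the drug and another to the disease. With six sites and two written rules, the AE record could also differ in completeness between sites.

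Section 3 names safety beside efficacy as an aim, so the completeness of the non-serious AE record matters even though the primary endpoint does not depend on it.

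**Working it through.** **Text comparison.** The plan states no figure here, so there is none to reproduce.

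| Place | Set of events implied |
|---|---|
| 8.2.1, definition and first rule | all AEs |
| 8.2.1, second rule | related AEs only |
| 3 (safety parameters), 8.4 (follow-up), 11.2 (periodic analysis) | all AEs |
| 7.3, visits 2 to 5 and week-1 call | drug effects |
| 8.2.3, closing summary | worded as effects of the drug |
| 8.2.2 and 11.2, serious events | all SAEs |

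The second rule applies the verb for recording, and not only the verb for reporting, to related events. Three sections need the full set and two lean towards the restricted set. None says which rule governs. Because SAEs carry no relatedness condition, the conflict concerns non-serious events.

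**Illustration of size.** Inputs from the documents: 29 patients per arm (section 3), and wheeze in 50% versus 15% in one of the earlier trials tabulated in section 6.3. Assumed: the share *s* of events judged related in each arm. The plan specifies no test of adverse events, so power is used only as a measure of lost information.

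Recorded rates: p1 = 0.50 × s(TIS), p2 = 0.15 × s(placebo).

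Power at two-sided 0.05, with p̄ = (p1 + p2)/2 and n = 29:

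Φ{ [ |p1 − p2| − 1.96·√(2p̄(1 − p̄)/n) ] / √[ (p1(1 − p1) + p2(1 − p2))/n ] }

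Full recording: p̄ = 0.325, so (0.35 − 1.96 × 0.1230)/0.1141 = 0.955, and Φ(0.955) ≈ 0.83.

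| Share judged related, TIS / placebo | Recorded, TIS vs placebo | Difference (points) | Ratio | Power |
|---|---|---|---|---|
| 100% / 100% | 50% vs 15% | 35 | 3.3 | 83% |
| 75% / 75% | 37.5% vs 11.25% | 26.25 | 3.3 | 65% |
| 50% / 50% | 25% vs 7.5% | 17.5 | 3.3 | 44% |
| 25% / 25% | 12.5% vs 3.75% | 8.75 | 3.3 | 23% |
| 50% / 25% | 25% vs 3.75% | 21.25 | 6.7 | 64% |
| 25% / 50% | 12.5% vs 7.5% | 5 | 1.7 | 9% |

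With equal shares the ratio stays at 3.3 and only events and precision are lost. The ratio changes only in the last two rows, where attribution differs by arm.

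**The case against.** The strongest defence is that the second sentence is one loosely worded phrase about the yearly report. The definition, the sentence before it, and sections 8.4 and 11.2 all fit that reading, and it is probably what was intended. It stands as a plausible reading. It does not settle the matter, because the sentence restricts recording in so many words and the visit lists point the same way.

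A reader might infer more than the documents support, in four respects:

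- *That the basis for stopping the trial is compromised.* The explicit trigger in section 8.5 reads "If adverse events of a particularly serious type are more common in the experimental arm compared to the control arm", and the comparison in section 11.2 concerns SAEs and SUSARs. SAEs are reported regardless of relatedness, so these triggers are largely intact.
- *That omitted events are lost for good.* Section 7.3 has changes in medical condition entered on the diary card, which is checked at every visit from week 13. Medical history and laboratory tests are also taken at each of those visits. Some events could be traced, although not in a form designed for comparing arms.
- *That the arm comparison is biased.* That needs attribution to differ by arm. Sections 6.5 and 6.8 describe identical sealed boxes, blinded investigators and opaque return bags. Section 6.5 also says that the ampoules differ in shape, so different attribution is possible, but the documents do not show that it occurs.
- *That week 56 has no safety assessment.* That visit keeps medical history, diary check, laboratory tests and spirometry; only an adverse-event line is absent.

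**Conclusion.** The contradiction is real and unresolved, and it should be corrected. Its reach is non-serious adverse events: a site following the second sentence would leave those judged unrelated out of the AE record. This weakens the periodic analysis in section 11.2, the by-arm review in section 8.5 and any final safety tables. Section 9 specifies no adverse-event analysis, so no planned test is invalidated.

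With the blind intact, the main effect is fewer events and less precision. The documents give no attribution rates. The range of about 65% down to 23% power, against 83% with full recording, rests on assumed shares of 75% to 25% and on event rates borrowed from one earlier trial. It shows scale and is not an estimate for this trial.

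**What to change.** - **Section 8.2.1:** delete the words *recorded and* from the second sentence. State that all adverse events during the study, in both arms, are entered in the e-CRF with relatedness as a separate field, and that only the yearly report is limited to related events. Keep the period as the whole study, as the definition does; starting at first dose would drop events from run-in procedures.
- **Section 7.3:** replace the line on potential side effects at visits 2 to 5 with *All adverse events will be recorded*, and add the same line at week 56. Copying the existing side-effects line to week 56 would only extend the restricted wording. The week-1 call item can be aligned at the same time.
- **Section 8.2.3:** reword the closing summary so that patients and physicians pass on all adverse events, and not only those seen as effects of the study drug.

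The cost is a short text correction and slightly more e-CRF entry. The diary card and visits already exist, and no treatment rule changes.
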